5.7. Multicenter Studies

For most analyses, data will be pooled across all clinical sites. While the sites use standardized procedures and rely on central laboratories for the assessment of immunogenicity endpoints, exploratory subgroup analyses of immunogenicity endpoints will be conditionally conducted within site-specific subgroups as specified in [Section 7.2](#).

5.8. Multiple Comparisons/Multiplicity

Analyses will be descriptive in nature. No adjustments for multiplicity are planned, but the number of comparisons made will be factored into the interpretation of results, as appropriate. No adjustment will be made for the interim analysis.

6. STUDY PARTICIPANTS

6.1. Demographic and Other Baseline Characteristics

Sex, race, ethnicity, age, prior receipt of seasonal influenza vaccination, and prior receipt of COVID-19 vaccination will be summarized by analysis group and site ([Table 10](#) [categorical characteristics] and [Table 11](#) [continuous characteristics]). Demographic characteristics will be detailed per participant ([Listing 7](#)).

6.2. Disposition of Participants

Screening failures will be listed ([Listing 5](#)) and summarized by reason and by cohort ([Table 7](#)). The disposition of participants in the study will be tabulated by analysis group. Disposition events to be summarized will be the total number of participants screened, enrolled/randomized, receiving at least 1 dose, receiving at least 2 doses (where applicable), completed safety follow-up for 7 days post-each dose, completed safety follow-up for 28 days post-each dose, completed safety follow-up through the end of the study, and terminated early from study ([Table 8](#)). A flowchart showing the disposition of study participants and the inclusion of participants in analyses, adapted from the Consort Statement, will be generated ([Figure 2](#)). This figure will present the number of participants screened, enrolled, randomized, receiving the protocol-defined number of study vaccinations, lost to follow-up, and analyzed, by analysis group.

The composition of analysis populations, including reasons for participant exclusion, will be presented by analysis group ([Table 9](#)).

The following participant listings will be generated:

- Listing of participants who received investigational product along with their intended randomized assignment, date of vaccine administration(s), and any relevant study product administration deviations ([Listing 1](#)).
- Listing of participants who discontinued dosing or terminated from study follow-up early along with the reason for early discontinuation/termination ([Listing 2](#)), including study terminations related to the COVID-19 pandemic as applicable.
- Listing of participants excluded from analysis populations ([Listing 6](#)).

6.3. Prior and Concurrent Medical Conditions

All current illnesses and past or pre-existing medical conditions will be coded using Medical Dictionary for Regulatory Activities (MedDRA®) version 26.1 or higher.

Summaries of participants' prior and concurrent medical conditions will be presented by analysis group and MedDRA® system organ class (SOC) for the Safety population ([Table 12](#)).

Individual participant listings will be presented for all reported medical history including prior and concurrent medical conditions ([Listing 8](#)).

6.4. Prior and Concomitant Medications

Prior (within 30 days of enrollment) and concomitant medications will be coded to the Anatomical Therapeutic Classification (ATC) using the WHO Drug Dictionary. The use of concomitant medications

during the study will be summarized by ATC1 and ATC2 code, as well as analysis group, for the Safety population ([Table 114](#)).

A listing of prior and concomitant medications by participant will be presented, with events corresponding to receipt of coronavirus 2019 (COVID-19) vaccine during the study period highlighted in green ([Listing 15](#)).

6.5. Prior Vaccinations

Vaccination history is obtained for all participants for the two years prior to enrollment. A listing of prior vaccinations will be presented, with events corresponding to seasonal influenza vaccine receipt and COVID-19 vaccine receipt highlighted in yellow and green, respectively ([Listing 9](#)).

6.6. Measurements of Study Product Compliance

Participants are directly observed at the time of dosing by a member of the clinical research team who is licensed to administer the study product. Participants in Cohorts 1, 2, and 3 receive one dose of study product and the remaining participants receive two doses of study product. The number of doses of study product administered to participants will be presented by analysis group as part of the participant disposition table ([Table 8](#)). Details of study product administration by participant will be provided ([Listing 1](#)).

6.7. Protocol Deviations

A summary of participant-specific protocol deviations will be presented by deviation category, deviation type, and analysis group for all enrolled participants ([Table 5](#)). A participant listing of all participant-specific protocol deviations and a listing of all non-participant specific protocol deviations will be generated ([Listing 3](#) and [Listing 4](#), respectively), including protocol deviations related to the COVID-19 pandemic as applicable.

7. IMMUNOGENICITY/IMMUNOLOGICAL EVALUATION

Immunogenicity analyses will be conducted in the modified intent-to-treat population. If sufficient data (>10% of secondary analysis timepoints) would be excluded by the PP exclusions, sensitivity analyses will be performed utilizing the PP population for secondary immunogenicity analyses.

Immunogenicity results will be listed with study days across columns ([Listing 10](#)).

7.1. Secondary Immunogenicity Analyses

Hemagglutination inhibition (HAI) and microneutralization (MN) antibody titers are measured in serum against A/Singapore/INFIMH-16-0019/2016. These antibody titers will be summarized by geometric mean titers (GMTs) and the percentage of participants reporting titers $\geq 1:40$ (defined as seroprotection for HAI) and associated 95% CIs, presented by analysis group at baseline and 28 days post last vaccination (Day 29 for Cohorts 1-3, Day 57 for Cohort 4). Geometric mean fold-rise (GMFR) and the percentage of participants reporting a fold-rise ≥ 2 and ≥ 4 from baseline and associated 95% CIs will also be presented for visits post baseline ([Table 13](#) and [Table 14](#) for HAI and MN, respectively). Titers will be presented graphically over time via line graphs displaying the GMT and associated 95% CIs for each analysis group with individual trajectories presented at a decreased transparency ([Figure 3](#) and [Figure 4](#) for HAI and MN in serum, respectively).

ECL signal, total sIgA concentration, and specific activity (as defined in [Section 3.3](#)) are measured in NLF supernatant by BAMA will be summarized at baseline, 28 days post last study vaccination, and 28 days post IIV4 administration, separately for each antigen. Arithmetic means and associated 95% CIs will be presented for ECL signal, total sIgA concentration, and specific activity by analysis group at baseline and 28 days post last vaccination (Day 29 for Cohorts 1-3, Day 57 for Cohort 4). Arithmetic mean difference from baseline and associated 95% CIs for ECL signal, total sIgA concentration, and specific activity will also be presented for visits post baseline ([Table 15](#) through [Table 18](#)). ECL signal, total sIgA concentration, and specific activity as measured by BAMA will be presented graphically over time, separately by antigen, via line graphs displaying the arithmetic mean and associated 95% CIs for each analysis group with individual trajectories presented at a decreased transparency ([Figure 5](#) through [Figure 7](#)).

7.2. Exploratory Immunogenicity Analyses

Hemagglutination inhibition (HAI) and microneutralization (MN) antibody titers as measured in serum will be summarized 28 days post IIV4 administration as described for the secondary immunogenicity endpoints corresponding to baseline and 28 days post last vaccination ([Table 13](#) and [Table 14](#) for HAI and MN, respectively). Titers at the visit corresponding to 28 days post last vaccination will be presented in the line graphs for each analysis group ([Figure 3](#) and [Figure 4](#) for HAI and MN in serum, respectively).

Hemagglutination inhibition (HAI), microneutralization (MN) antibody titers and neuraminidase inhibition (NAI) titers are measured in plasma against A/Singapore/INFIMH-16-0019/2016. These titers will be summarized by GMTs and the percentage of participants reporting titers $\geq 1:40$ (defined as seroprotection for HAI) and associated 95% CIs, presented by analysis group at baseline, 28 days post last vaccination (Day 29 for Cohorts 1-3, Day 57 for Cohort 4), and 28 days post IIV4 administration. GMFR and the percentage of participants reporting a fold-rise ≥ 2 and ≥ 4 from baseline and associated 95% CIs will also be presented for post baseline visits ([Table 19](#) through [Table 21](#)). Titers will be presented graphically over time via line graphs displaying the geometric mean and associated 95% CIs for each analysis group with individual trajectories

presented at a decreased transparency ([Figure 8](#), [Figure 9](#), and [Figure 10](#) for HAI, MN, and NAI in plasma, respectively).

sIgA titers, total sIgA concentration, and normalized sIgA in NLF supernatant against A/Singapore/INFIMH-16-0019/2016 as measured by ELISA (as defined in [Section 3.3](#)) will be summarized at baseline, 28 days post last study vaccination, and 28 days post IIV4 administration. Arithmetic means and associated 95% CIs for total sIgA concentration and normalized sIgA and GMTs and associated 95% CIs for sIgA titers will be presented by analysis group at baseline, 28 days post last vaccination (Day 29 for Cohorts 1-3, Day 57 for Cohort 4), and 28 days post IIV4 administration. Arithmetic mean difference from baseline and associated 95% CIs for total sIgA concentration and normalized sIgA, and GMFR and the percentage of participants reporting a fold-rise ≥ 2 and ≥ 4 from baseline and associated 95% CIs will be presented for visits post baseline ([Table 22](#)). sIgA titers, total sIgA concentration, and normalized sIgA as measured by ELISA will be presented graphically over time via line graphs displaying the (geometric or arithmetic, as appropriate) mean and associated 95% CIs for each analysis group with individual trajectories presented at a decreased transparency ([Figure 11](#) through [Figure 13](#)).

The effects of age, dose level, sex, clinical site, prior receipt of seasonal influenza vaccine(s) within 2 years of first study vaccination, prior receipt of COVID-19 vaccine(s) within 2 years of first study vaccination, and seroprotection (i.e., HAI titer $\geq 1:40$ against A/Singapore/INFIMH-16-0019/2016 [H3N2]) at baseline on humoral immunogenicity directed against homologous viral strains will be conditionally analyzed. Subgroup immunogenicity analyses may be performed if and only if, for at least one analysis group, the CIs of the change from baseline parameter (i.e., GMFR or mean difference from baseline) at the visit 28 days post-last vaccination do not overlap between the corresponding vaccine and placebo groups and sufficient data for each subgroup are available. If subgroup analyses are performed, each subgroup within an analysis group will be summarized separately (e.g., male participants receiving vaccine in Cohort 1, male participants age 9-17 receiving placebo in Cohort 1, female participants age receiving vaccine in Cohort 1, female participants receiving placebo in Cohort 1, etc.). Subgroups will be defined as the following:

- Age: 2-4 years old, 5-8 years old, and 9-17 years old
- Dose level: 10^8 TCID₅₀ and 10^9 TCID₅₀ (regardless of number of doses)
- Sex: male and female
- Clinical site: Duke University, University of Maryland, University of Maryland (Frederick), Vanderbilt University, and University of Iowa
- Prior receipt of seasonal influenza vaccine(s) within 2 years of first study vaccination: prior receipt of seasonal influenza vaccine(s) ≤ 1 year prior to first study vaccination,* prior receipt of seasonal influenza vaccine(s) 1-2 years prior to first study vaccination,* and no prior receipt of seasonal influenza vaccine(s)*
- Prior receipt of COVID-19 vaccine(s) within 2 years of first study vaccination: prior receipt of COVID-19 vaccine(s) ≤ 1 year prior to first study vaccination,* prior receipt of COVID-19 vaccine(s) 1-2 years prior to first study vaccination,* and no prior receipt of COVID-19 vaccine(s)*
- Seroprotection at baseline: plasma HAI titer $\geq 1:40$ against A/Singapore/INFIMH-16-0019/2016 [H3N2] at baseline and plasma HAI titer $< 1:40$ against A/Singapore/INFIMH-16-0019/2016 [H3N2] at baseline

*Any prior receipt (limited to two years prior to enrollment) may be utilized as a subgroup if there are insufficient data for subgrouping by timing of receipt.

An example table shell for an age subgroup summary of HAI antibody titers in serum is presented in [Table 23](#); additional subgroup analyses would follow a similar shell with the same variables presented as the corresponding shell from the secondary or exploratory endpoint. Figures will similarly present subgroups following the corresponding shell from the secondary or exploratory endpoint if such subgroup analyses are performed. Results from subgroup analyses, if performed, will be hypothesis generating.

Additional exploratory immunogenicity assessments include T-cell immune response, serum antibody response against homologous and heterologous viral strains, and additional humoral or mucosal immune responses, as described in [Section 3.2](#). TFL shells for these endpoints will be included in an addendum to the SAP, after details for the data are finalized.

8. SAFETY EVALUATION

All summaries and analyses of safety data will be presented for the Safety population. Summaries of placebo groups will include all participants from applicable cohorts of the same age (i.e., placebo recipients in Cohorts 2, 3, and 4 will be combined) for post-first dose and overall analyses, unless otherwise specified. Solicited events occurring in the vaccine from Cohorts 3 and 4 will be combined for post-first dose analyses and summarized separately after the second dose in Cohort 4. The denominator for percentages will be based on the number of non-missing observations for an assessment or based on the number of participants in the Safety population, unless otherwise specified.

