The first two groups to be vaccinated will be Cohorts 1 and 2. Cohort 1 consists of 45 children 9–17 years old. Thirty of them will receive one dose of the vaccine at a dose of 10^9 TCID₅₀, and 15 will receive one dose of placebo. Cohort 2 comprises 45 children 2–8 years old. Thirty of them will receive one dose of the vaccine at a dose of 10^8 TCID₅₀ and 15 will receive one dose of placebo. Sites will enroll participants into Cohorts 1 and 2 simultaneously. Once 25 or more participants in each of the first 2 cohorts (Cohorts 1 and 2) have completed Day 8, the SRC will evaluate if any halting rules are met and if it is deemed safe, enrollment in Cohort 3 may open. Enrollment within each cohort will not halt during the SRC review. Cohort 2 must fully enroll before enrollment in Cohort 3 may begin. If any halting rules are met or if the SRC raises any safety concerns other than halting rules that should be independently reviewed, the external Safety Monitoring Committee (SMC) will meet to discuss the data prior to progression to the next cohort.

Cohort 3 consists of 25 children 2–8 years old. Fifteen of them will receive one dose of vaccine at 10^9 TCID₅₀ and 10 will receive one dose of placebo. Once all 25 participants in Cohort 3 have completed Day 8 of follow-up, similar to Cohorts 1 and 2, the SRC will review to ensure no

halting rules are met and if no rules are met and the SRC determines it is safe to proceed, simultaneous enrollment into Cohorts 4 and 5 can begin. If any halting rules are met or any concerns are raised by the SRC, an external SMC may meet to discuss the data for recommendations on either progression or clinical trial modification before progression to the next cohort.

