Individual placebo group or Cohort 3-4 vaccine group (N=15)	0 (0, 21.8)	26.7 (7.8, 55.1)	33.3 (11.8, 61.6)	46.7 (21.3, 73.4)	60 (32.3, 83.7)	80 (51.9, 95.7)	100 (78.2, 100)	-	-
Individual vaccine group in Cohorts 6-7 (N=18)	0 (0, 18.5)	22.2 (6.4, 47.6)	27.8 (9.7, 53.5)	38.9 (17.3, 64.3)	50 (26, 74)	66.7 (41, 86.7)	83.3 (58.6, 96.4)	-	-
Cohorts 1-2safety review (N=25)	0 (0, 13.7)	16 (4.5, 36.1)	20 (6.8, 40.7)	28 (12.1, 49.4)	36 (18, 57.5)	48 (27.8, 68.7)	60 (38.7, 78.9)	-	-
Individual vaccine group in Cohorts 1-2; Cohorts 3-4 aggregate vaccine groups, post first-dose (N=30)	0 (0, 11.6)	13.3 (3.8, 30.7)	16.7 (5.6, 34.7)	23.3 (9.9, 42.3)	30 (14.7, 49.4)	40 (22.7, 59.4)	50 (31.3, 68.7)	-	-
Any Sing2016 M2SR H3N2 Vaccine, Cohorts 1-4 (N=90)	0 (0, 4)	4.4 (1.2, 11)	5.6 (1.8, 12.5)	7.8 (3.2, 15.4)	10 (4.7, 18.1)	13.3 (7.1, 22.1)	16.7 (9.6, 26)	50 (39.3, 60.7)	73.3 (63, 82.1)

Any									
Sing2016	0								
M2SR H3N2	(0,	3.0	3.8	5.3	6.8	9.1	11.4		50.0
Vaccine	2.8	(0.8,	(1.2,	(2.2,	(3.2,	(4.8,	(6.5,		(41.2,
(N=132))	7.6)	8.6)	10.6)	12.5)	15.3)	18)	-	58.8)

For illustration, if zero events of a certain type were observed in an individual vaccine group or in Cohorts 3-4 aggregate vaccine groups after one dose with N=30 participants, true event probabilities above 11.6% could be ruled out at the $\alpha=0.025$ level, compared to 2.8% in the combined vaccine groups (N=132). Binomial confidence intervals are widest at 50% events observed; the estimates associated with approximately (or exactly) 50% observed events are bolded in [Table 6](#). Within an individual vaccine group or in Cohorts 3-4 aggregate vaccine groups after one dose with N=30 participants, the maximum half-width for a 95% CI would be 18.7%, compared to 10.7% across active vaccine groups in Cohorts 1-4. In the case of substantial loss to follow-up or missed visits, these estimates give an idea of the loss of precision due to decreasing the effective sample size.

While no formal hypothesis testing is planned for this study, some limited statistical testing may be conducted to aid interpretation of the strength of the results. Comparisons would be primarily focused on vaccine to placebo within a given cohort, due to the likelihood of confounding in most results due to age, dose level, or the number of doses (see [Section 9.4.1](#) for details on analysis groupings).

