9.4.2 Analysis of the Primary Endpoint(s)

The primary objective of the study is to assess the safety and tolerability of 1 or 2 doses of the study vaccination, as determined by the incidence of solicited reactogenicity events, unsolicited

serious and non-serious adverse events, adverse events of special interest, and new-onset chronic medical conditions.

Safety objectives will be assessed in the Safety population. The vaccine and placebo groups from Cohorts 3 and 4 will be combined for post-first dose analyses and presented separately after the second dose in Cohort 4. Solicited local and systemic reactogenicity events will be summarized via the number and percentage of participants reporting each event, and any solicited reactogenicity event, within the 7 days following each dose in each group. These will be tabulated by severity, by dose, and post-any dose. Exact 95% Clopper-Pearson confidence intervals for the probability of each event post-each and any dose will be computed for each group. The frequency of each solicited event will be summarized as well. Severity will be determined as described in [Section 8.4.3](#).

Non-serious unsolicited adverse events and adverse events of special interest occurring within the 28 days post-each dose and post-either dose will be summarized by MedDRA system organ class (SOC) and preferred term (PT), severity, and dose, as well as post-any dose. Serious adverse events and new-onset chronic medical conditions reported through the end of the study period will be summarized similarly. Abnormal clinical laboratory values will be considered unsolicited adverse events and graded as in [Section 8.4.2](#), and these will be summarized separately. For unsolicited events, summaries will also be made by relationship to study vaccine, as described in [Section 8.4.4](#).

Adverse events and clinical laboratory results will be presented in data listings as well.

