3.2. Endpoints

Primary

- (Safety) The number and percentage of study participants in Cohorts 1-4 each and across Cohorts 1-4 who experience solicited local reactogenicity events, of all severity grades and by grade, in the 7 days following administration of each dose of vaccine
- (Safety) The number and percentage of study participants in Cohorts 1-4 each and across Cohorts 1-4 who experience solicited systemic reactogenicity events, of all severity grades and by grade, in the 7 days following administration of each dose of vaccine
- (Safety) The number and percentage of study participants in Cohorts 1-4 each and across Cohorts 1-4 who experience unsolicited non-serious adverse events, of all severity grades and by grade, in the 28 days following administration of each dose of vaccine
- (Safety) The number and percentage of study participants in Cohorts 1-4 each and across Cohorts 1-4 who experience adverse events of special interest (AESIs) from the time of first vaccination through the end of the study period (final visit in the month of April of the calendar year following enrollment)
- (Safety) The number and percentage of study participants in Cohorts 1-4 each and across Cohorts 1-4 who experience Serious Adverse Events (SAEs) from the time of first vaccination through the end of the study period (final visit in the month of April of the calendar year following enrollment)
- (Safety) The number and percentage of study participants in Cohorts 1-4 each and across Cohorts 1-4 who experience new-onset chronic medical conditions (NOCMCs) from the time of the first study vaccination through the end of the study period (final visit in the month of April of the calendar year following enrollment)

Secondary

- (Immunogenicity) The number and percentage of participants in Cohorts 1, 2, and 3 with putative seroprotection at baseline (Day 1) and on approximately Day 29, defined as an HAI titer $\geq 1:40$ in serum against an H3N2 M2SR-like virus
- (Immunogenicity) The number and percentage of participants in Cohort 4 with putative seroprotection at baseline (Day 1) and on approximately Day 57, defined as an HAI titer $\geq 1:40$ in serum against an H3N2 M2SR-like virus
- (Immunogenicity) The number and percentage of participants in Cohorts 1, 2, 3 with neutralization titer $\geq 1:40$ in serum against an H3N2 M2SR-like virus on approximately Day 29

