8.1.1.2. Solicited Events/Symptoms

Participant-level summaries of solicited AE data will be generated for solicited events applicable to each participant based on their age at enrollment. For summaries by severity, the maximum severity over 7 days post applicable vaccinations will be identified for each participant. For summaries independent of severity, a participant will be classified as reporting the event if their maximum severity for the event was classified as mild or worse. Denominators for percentages will be the number of participants with solicited data available for the given solicited event in the specified group for which the solicited event is applicable. All placebo participants ages 2-8 years old will be summarized together, except for events post dose 2, and solicited events of vaccine recipients post first study vaccination in Cohorts 3 and 4 will be summarized together.

The number and percentage of participants reporting any solicited event, any local event, any systemic event, and each applicable solicited adverse event individually will be summarized by maximum severity and vaccination group, separately for each vaccination and after any vaccination ([Table 26](#) through [Table 28](#)) and presented graphically in a bar chart ([Figure 14](#) through [Figure 23](#)).

The number of participants reporting a solicited adverse event will be summarized by day post vaccination for each vaccination and after any vaccination ([Table 29](#) through [Table 39](#)) and presented graphically in a bar chart ([Figure 24](#) through [Figure 33](#)).

All reported solicited events will be presented in participant listings separately for local events ([Listing 11](#)) and systemic events ([Listing 12](#)).

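### Post-dose-1 safety tables for 2-8-year-olds set each vaccine group against placebo pooled over Cohorts 2-4, and the solicited-event tables omit the promised exact CIs; SAP Section 11 records neither change

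*SAP*

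**What the plan says.** **Pooling.** SAP Section 8 states that "placebo recipients in Cohorts 2, 3, and 4 will be combined) for post-first dose and overall analyses, unless otherwise specified". For solicited events, SAP 8.1.1.2 adds: "All placebo participants ages 2-8 years old will be summarized together, except for events post dose 2". On the vaccine side the SAP pools less widely: "Solicited events occurring in the vaccine from Cohorts 3 and 4 will be combined for post-first dose analyses". The Table 26 shell therefore has one placebo column for ages 2-8. It stands beside a 10^8 column (Cohort 2) and a combined 10^9 column (Cohorts 3 and 4). Tables 31-33, 42-44 and 77-79 and Figures 15, 20, 25, 30, 35 and 49 use the same grouping.

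Protocol 9.4.2 is narrower: "The vaccine and placebo groups from Cohorts 3 and 4 will be combined for post-first dose analyses". It does not bring in Cohort 2 placebo. Protocol 9.2 adds: "Comparisons would be primarily focused on vaccine to placebo within a given cohort, due to the likelihood of confounding".

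**Endpoint.** The first primary endpoint in SAP 3.2 is "The number and percentage of study participants in Cohorts 1-4 each and across Cohorts 1-4 who experience solicited local reactogenicity events", overall and by grade.

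**Order of enrolment.** Protocol 1.1 states: "Cohort 2 must fully enroll before enrollment in Cohort 3 may begin". Protocol 4.1 likewise opens Cohort 4 only after Cohort 3 has enrolled, and SAP 4.1 confirms that enrolment was sequential.

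**Confidence intervals.** For solicited events Protocol 9.4.2 promises: "Exact 95% Clopper-Pearson confidence intervals for the probability of each event post-each and any dose will be computed for each group". SAP 8.1.1.2 does not mention them, and the shells for Tables 26-28 carry only counts and percentages.

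**Declared changes.** SAP Section 11 lists the stop before Cohorts 5-7 and the dropped quartiles, and nothing else.

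**The concern.** In a descriptive Phase 1b trial, the side-by-side columns are the primary safety result. Runny nose, cough, sore throat and fever depend on what is circulating, so the value of a placebo column lies in its being randomised together with the vaccine group beside it. Pooling across sequential cohorts partly gives that up. A difference in background illness between enrolment periods can then show up as a vaccine effect, with opposite signs at the two dose levels.

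The AESI, SAE and NOCMC tables raise a further point. They show Cohort 3 (one dose) and Cohort 4 (two doses) separately against the pool, for example in Tables 54-56. Active surveillance for wheezing runs for 28 days after each dose. Two-dose vaccine recipients therefore have two such windows, while the 25 pooled placebo children from Cohorts 2 and 3 have one.

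The missing CIs are a separate defect. With groups this small, a bare percentage tells the reader little about what has been ruled out.

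**Working it through.** **Inputs.** Planned sizes from Protocol Table 2 (repeated in SAP Table 2), vaccine:placebo: Cohort 2, 30:15; Cohort 3, 15:10; Cohort 4, 15:10. The documents give neither actual numbers per arm nor background event rates.

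**1. The plan's own precision figures.** Exact two-sided 95% Clopper-Pearson limits reproduce them:
- 0/30: upper limit 1 - 0.025^(1/30) = 11.6%
- 15/30: 31.3% to 68.7%, half-width 18.7 points
- 45/90: 39.3% to 60.7%, half-width 10.7 points

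**2. Who the pooled controls are.** Pool = 15 + 10 + 10 = 35.
- Cohort 2 (10^8) column: own-cohort 15/35 = 42.9%; from other cohorts 20/35 = 57.1%
- Combined Cohort 3+4 (10^9) column: own-cohort 20/35 = 57.1%; from Cohort 2 15/35 = 42.9%
- Cohort 3 or Cohort 4 shown singly (AESI, SAE, NOCMC tables): own-cohort 10/35 = 28.6%; from other cohorts 25/35 = 71.4%

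The protocol's combination of Cohorts 3 and 4 does not have this problem. Both cohorts have the same 15:10 ratio, so each supplies half of the vaccine arm (15/30) and half of the placebo arm (10/20).

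**3. Effect of a background difference.** Assume the vaccine has no effect, the background rate is b in Cohort 2, and it is b + d in Cohorts 3 and 4. The expected pooled placebo rate is (15b + 20(b + d))/35 = b + (20/35)d. The contrasts with placebo then shift as follows:
- 10^8: b - [b + (20/35)d] = -(20/35)d
- 10^9: (b + d) - [b + (20/35)d] = +(15/35)d

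| d (assumed) | 10^8 shift | 10^9 shift |
|---|---|---|
| 5 points | -2.9 | +2.1 |
| 10 points | -5.7 | +4.3 |
| 20 points | -11.4 | +8.6 |

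The signs reverse if the background is higher in Cohort 2. Against own-cohort placebo the expected shift is zero.

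**4. Precision given up by not pooling.** Placebo column, exact 95% limits:
- N=15: upper limit with no events 21.8%; half-width 26.1 points at 7/15
- N=20: 16.8%; 22.8 points at 10/20
- N=35: 10.0%; 17.3 points at 17/35

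**5. What own-cohort view remains in the shells.**
- Table 24 shows each cohort with its own placebo, but only as at-least-one counts; it grades related events as a class, not solicited symptoms.
- Table 25 also keeps own-cohort placebo and lists each solicited or unsolicited term reaching 5% in any group, without grade. One report in a group of 10 (10.0%) or 15 (6.7%) is enough. Only a symptom seen at most once in each group of 30 (3.3%), and in no smaller group, would drop out.
- Tables 27-28 use Cohort 4 vaccine and placebo only.

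What is missing after dose 1 is the result by symptom and by grade for the 2-8-year cohorts beside their own placebo.

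**The case against.** The strongest defence has four parts.

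- **Permission.** Protocol 9.4.1 lets the analysis plan specify further groupings, so adding a pooled column is not in itself a breach. That stands. However, the SAP replaces the planned placebo grouping in these tables, and Section 11 does not say so.
- **Reasons for confounding.** The Protocol 9.2 sentence names age, dose level and number of doses, and it concerns optional testing. After dose 1, placebo children in Cohorts 2-4 share an age band, have no dose level and have had one administration. So the protocol's own reasons do not count against pooling at that point. Calendar time does, although that sentence does not name it. In the AESI, SAE and NOCMC tables the number of doses counts as well.
- **Precision.** The pool is tighter, and at N=15 the half-width (26 points) exceeds any shift computed above. This supports keeping the pooled column, but not showing it alone.
- **Existing outputs.** Tables 24-25 give a concurrent view, Cohort 1 always has its own placebo, and SAP 5.8 calls the analyses descriptive. All true, and this limits the severity.

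A reader might infer more than the documents support:
- That every 2-8-year vaccine group faces mostly non-concurrent controls. In the post-dose-1 tables this holds for the 10^8 column only.
- That pooling creates a false dose gradient. The gap between the two vaccine columns is the same whichever placebo column is shown; pooling hides the explanation for it.
- That the SAP abandons CIs. SAP 5.1 keeps the Clopper-Pearson rule for binary variables, and the Table 40 shell has a CI column. The gap is in the solicited-event text and shells.

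**Conclusion.** The point holds at should-fix level. For post-dose-1 events in 2-8-year-olds, the SAP widens the protocol's placebo pooling to include Cohort 2. It thereby removes the randomised, concurrent comparator from the by-symptom, by-grade tables. At planned sizes 57% of the controls beside the 10^8 group, and 43% of those beside the combined 10^9 group, come from other cohorts. Where Cohorts 3 and 4 are shown singly, the figure is 71%, with mixed one- and two-dose follow-up.

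The size of any distortion cannot be known from the documents. At an assumed 10-point background difference it is about 4 to 6 points, in opposite directions for the two dose levels. This rests on planned cohort sizes, one common background for Cohorts 3 and 4, and no vaccine effect. Actual enrolment may differ slightly.

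The absent exact CIs for solicited events are a separate departure from Protocol 9.4.2. SAP Section 11 records neither. Neither invalidates a test, since no formal testing is planned.

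**What to change.** - **Tables 26, 31-33, 42-44 and 77-79, and Figures 15, 20, 25, 30, 35 and 49:** show Cohort 2 placebo (N=15) beside the 10^8 group and Cohort 3+4 placebo (N=20) beside the 10^9 group as the main comparators. Keep the pooled N=35 summary as a labelled supplement.
- **AESI, SAE and NOCMC tables and figures:** show own-cohort placebo beside each vaccine group.
- **Tables 26-28:** add exact 95% Clopper-Pearson CIs. Tables 27-28 need nothing else, because they are not pooled.
- **SAP Sections 8 and 8.1.1.2:** align the wording with these groupings.
- **SAP Section 11:** record any departure from Protocol 9.4.2 that remains.

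Cost: edits to text and shells, more columns, and no new data. The main placebo columns have wider intervals (maximum half-width about 26 points at N=15 and 23 at N=20, against 17 at N=35). The supplementary pooled summary keeps the tighter figure available.
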